#### 6.3.3. Method of Implementing the Treatment Arm Allocation

Randomisation will be performed by computer using a minimisation algorithm, stratified by the following variables:

- institution
- type of breast surgery (BCS or mastectomy)
- receptor status (triple negative, HER2+, ER/PR+ and HER2-)

The randomisation system will ensure that there is no bias between the two trial groups. Participants will be randomised strictly sequentially, and allocation between trial arms will be in a 1:1 ratio. The computer minimisation programme will be developed and held centrally at the WCTU.

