## **10.2. Planned Recruitment Rate**

ATNEC will randomise 1900 participants from approximately 100 centres across the UK over 5 years. Based on a survey of UK practice, it is anticipated that each hospital will recruit five participants per year. A 50% participant uptake rate of those eligible is assumed.

An 18-month internal feasibility phase has been incorporated into the trial to assess the willingness of clinicians and patients to participate. The criteria for progressing from the internal feasibility phase at 18 months to the main trial are based on site opening, recruitment and compliance to allocated intervention and use a traffic light system of green for continuing to recruit, amber for considering amending the trial to improve recruitment either in terms of relaxing the eligibility, extending the number of sites and red for considering stopping the trial if there are no possible recovery options.

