#### 10.3.3. Statistical Methods

Time to event outcomes, including the co-primary outcome of DFS, will be assessed using Kaplan-Meier curves and compared using Cox proportional hazards models. Hazard ratio (forest) plots will be constructed for the stratification variables and important prognostic factors. A sensitivity analysis will be carried out adjusting for stratification variables (institution, type of breast surgery, receptor status). Exploratory subgroup analyses will be performed for those having ALND or ART.

The proportion of patients experiencing lymphoedema at five years will be compared across trial arms using a chi-squared test and a logistic regression model used to adjust for stratification variables. Arm morbidity, arm function and QoL will be scored using the appropriate manuals and assessed using a longitudinal mixed model regression analysis if model assumptions valid or a standardised area-under-the-curve analysis. Consideration will be given to any missing data in the form of a sensitivity analysis to determine the degree to which the conclusions may change with different missing data assumptions and mechanism models.

All analyses will be carried out on an intention-to-treat basis to preserve randomisation, avoid bias from exclusions and preserve statistical power. Thus, all subjects randomised into the study regardless of whether they receive the study intervention will be analysed unless they withdrew consent for further follow-up. The success of no axillary treatment relies on the confirmation of both non-inferiority in DFS and at least a 5% reduction in the proportion of participants with lymphoedema. No adjustment for multiple testing has been incorporated.

A Statistical Analysis Plan (SAP) will be developed to provide full details of the planned analysis.

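### The Cox model that decides DFS non-inferiority omits the minimisation factors, and the deciding lymphoedema analysis is not named

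*Protocol*

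**What the plan says.** **Allocation.** Protocol section 6.3.3: "Randomisation will be performed by computer using a minimisation algorithm, stratified by the following variables", followed by institution, type of breast surgery and receptor status; "allocation between trial arms will be in a 1:1 ratio". The Study Summary and section 10.3.1 list the same three factors.

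**DFS.** Section 10.3.3: "Time to event outcomes, including the co-primary outcome of DFS, will be assessed using Kaplan-Meier curves and compared using Cox proportional hazards models". No covariates are named for that comparison. The three factors come in only afterwards: "A sensitivity analysis will be carried out adjusting for stratification variables (institution, type of breast surgery, receptor status".

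**Lymphoedema.** Section 10.3.3 says the five-year proportion "will be compared across trial arms using a chi-squared test and a logistic regression model used to adjust for stratification variables". The two methods share one sentence and are not ranked.

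**Success rule.** Section 10.3.3: "The success of no axillary treatment relies on the confirmation of both non-inferiority in DFS and at least a 5% reduction" in the proportion with lymphoedema.

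**Sites.** Section 10.2: "ATNEC will randomise 1900 participants from approximately 100 centres across the UK over 5 years". Section 10.3.3 lists institution beside the other two factors without saying how it enters a model, and leaves full details to the SAP.

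**The concern.** An analysis should normally reflect the way patients were allocated. Here three factors are thought important enough to balance on, but the confidence interval that decides DFS non-inferiority does not use them. In a Cox model, leaving out a prognostic factor pulls the estimated hazard ratio toward 1. In a superiority trial that is conservative. In a non-inferiority trial it makes a worse arm look closer to control.

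This is not a detail left open for the SAP. The protocol itself gives the adjusted DFS model sensitivity status, and an SAP that made it primary would depart from section 10.3.3.

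For lymphoedema, success depends on both outcomes, yet two analyses are named and either could be taken as decisive. The logistic model gives an odds ratio, while the success rule is a difference in proportions.

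**Working it through.** **1. The plan's own figures.**
- DFS: control 90%, margin 3.5 points, one-sided 5%, power 85% (section 10.1). Hazard ratio at the margin = ln(0.865)/ln(0.90) = 1.376. Events = 4(1.645 + 1.036)²/(ln 1.376)² = 4 × 7.19/0.102 = 282, as stated in section 10.6.
- Lymphoedema: 11% v 6%, two-sided 5%, power 90%. The two-proportion formula with continuity correction gives 692 per arm (Table 1: 691). 692/0.75 = 923 per arm, or 1846 in total, as in Table 1.

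Both are unadjusted two-group calculations.

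**2. Events per site**, with 1900 participants and about 100 sites (19 per site):
- DFS: 282/100 = 2.8.
- Lymphoedema: 1900 × 0.75 = 1425 analysed; mean rate (11% + 6%)/2 = 8.5%; 1425 × 0.085 = 121 cases; 121/100 = 1.2.

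**3. What omission does.** Trials were simulated with 1900 participants minimised over 100 unequal sites, five years' accrual and 4.5 to 9.5 years' follow-up. The documents give no prognostic effects, so two settings were assumed:
- moderate (2300 runs): log hazard ratio 0.6 for the worst receptor group and 0.3 for surgery; log odds ratio 0.5 for surgery; site SD 0.4 for lymphoedema and half that for DFS;
- strong (3500 runs): 1.2, 0.6, 1.0 and 0.8 respectively.

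Site-size spread (gamma, shape 2), minimisation probability (0.8) and factor prevalences were also assumed. Monte Carlo standard error is about 0.4 to 0.5 points on type I error and 0.4 to 0.8 on power.

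| Moderate / strong | Unadjusted | Surgery + receptor |
|---|---|---|
| DFS mean log HR (true 0.320) | 0.317 / 0.303 | 0.320 / 0.313 |
| DFS one-sided type I error at margin | 5.8% / 6.0% | 5.7% / 5.3% |
| DFS power at HR 1 | 82.3% / 82.6% | 82.4% / 81.9% |
| Lymphoedema two-sided type I error | 5.1% / 4.1% | 5.1% / 4.4% |
| Lymphoedema power | 93.3% / 93.9% | 93.3% / 94.1% |

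Simulated DFS power is below 85% in both columns because, with both arms at 90%, about 260 events are expected among 1900 participants. The comparison between columns is what matters here.

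**4. If institution were entered as one fixed effect per site.** DFS power would be 80.7% / 79.5%. Lymphoedema type I error would be 5.8% / 5.6%, and the mean log odds ratio −0.73 / −0.78, against −0.67 / −0.68 with surgery and receptor status only. Part of that last gap may arise because an odds ratio conditional on site is a different quantity. The protocol does not say that institution would be entered this way.

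**The case against.** The strongest reply is that little changes. Under moderate effects, adjustment moves DFS type I error from 5.8% to 5.7%, which is within simulation error, and power hardly moves in any setting. That stands, and it limits the weight of the point.

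A second reply also has force. The DFS margin is an absolute 3.5 points, a population-level quantity, while an adjusted hazard ratio is conditional on the factors. The simulated error rates read 1.376 as a conditional hazard ratio, so part of the excess reflects that choice. The link between margin and model should therefore be stated.

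Several stronger readings are tempting but not supported:
- A reader might infer that both co-primary outcomes are decided unadjusted. For lymphoedema this is plausible, since the chi-squared test comes first and Table 1 is unadjusted, but the protocol does not say it.
- A reader might infer that the adjusted models will lose whole sites, or that DFS power collapses under stratification by every combination of site, surgery and receptor status. Both depend on a form of model that section 10.3.3 does not specify and the SAP may settle otherwise.
- A reader might infer that ignoring the factors overstates the standard error. That roughly fits the chi-squared test under strong effects (4.1%). It does not describe the Cox model, where the estimate is attenuated and the error rate is slightly too high.
- A reader might infer that leaving out LBCQ status at randomisation is an error. It is an efficiency choice.

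**Conclusion.** The point holds in a limited form. By clear implication the deciding DFS model omits all three minimisation factors, and the deciding lymphoedema analysis is not fixed.

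The excess in one-sided DFS type I error is at most about 1 percentage point (6.0% against 5%), and that figure needs strong assumed prognostic effects. Adjusting for surgery and receptor status brings it to 5.3%. For lymphoedema the choice of analysis hardly affects power or error rates; the issue is that the decision rule is ambiguous. Neither analysis is invalidated.

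The low event counts per site follow directly from the protocol's figures. They are a reason to state how institution is handled, not evidence that the planned model is wrong. The change is worth making because it costs almost nothing and, where it matters, moves the non-inferiority test in the safe direction.

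**What to change.** Amend Protocol section 10.3.3, and match it in the SAP, as follows:

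1. **DFS:** make the primary analysis a Cox model stratified by, or adjusted for, type of breast surgery and receptor status. State the hazard ratio margin that applies to this model and how it relates to the 3.5-point margin.
2. **Lymphoedema:** name one deciding analysis, a model with the same two factors, and report it as a risk difference with its confidence interval so that it matches the 5% success rule.
3. **Supportive analyses:** keep the unadjusted Cox model and the chi-squared test.
4. **Institution:** wherever it is adjusted for, use a random effect or shared frailty, or pool small sites under a rule fixed in advance. Do not use one fixed effect per site.
5. **Optional:** add LBCQ status at randomisation to the lymphoedema model.

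The cost is wording only, since every variable is already collected. Make the change before outcome data are examined by arm, because a later switch of primary model would look data-driven.

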## **STUDY SUMMARY**

Study Title:	ATNEC - Axillary management in T1-3N1M0 breast cancer patients with needle biopsy proven nodal metastases at		
	presentation after neoadjuvant chemotherapy.		
Sponsor Study Reference:	DHRD/2017/130		
Study Design:	A multi-centre phase III randomised controlled trial with embedded economic evaluation in which participants will be randomised in a 1:1 ratio.		
Study Participants:	T1-3N1M0 breast cancer patients aged 18 years or older, with needle biopsy proven nodal metastases, who after neoadjuvant chemotherapy (NACT) have no residual cancer in the lymph nodes on dual tracer sentinel node biopsy and removal of at least 3 lymph nodes (sentinel nodes and marked involved node).		
Planner Number of Sites:	~100		
Planned Sample Size:	1900 (950 per arm)		
Stratification	
 
Institution
 
Type of breast surgery (breast conserving surgery (BCS) vs mastectomy)
 
Receptor status (triple negative vs HER2 positive vs ER status positive and/or PR status positive and HER2 negative)
 
		
Intervention:	Participants in the experimental arm will not receive further axillary treatment (axillary lymph node dissection [ALND] or axillary radiotherapy [ART]), after NACT and surgery.		
Comparison/Control:	Participants in the control group will receive further axillary treatment (ALND or ART) after NACT and surgery, as per local guidelines.		
Follow Up Duration:	At least 5 years		
Planned Recruitment Start Date:	01 March 2021		
Planned Recruitment End Date:	01 March 2026		
Planned Study End Date:	28 February 2030		
Research Question/ Aims:	To assess whether, omitting further axillary treatment (ALND and ART) for patients with early stage breast cancer and axillary nodal metastases on needle biopsy, who after NACT have no residual cancer in the lymph nodes on sentinel node biopsy, is non-inferior to axillary treatment in terms of disease free survival (DFS), and reduces the risk of lymphoedema at 5 years.		

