## 1. BACKGROUND

There are around 55,000 new cases of breast cancer diagnosed each year. Axillary ultrasound, with needle biopsy of suspicious lymph nodes, is used in the initial diagnostic work-up of breast cancer patients. Patients with needle biopsy proven positive nodes are increasingly referred for neoadjuvant chemotherapy (NACT) to shrink the cancer before surgery. Currently after chemotherapy, all patients then undergo breast surgery (lumpectomy to remove the cancerous lump or mastectomy to remove the breast) and treatment to their axilla, either removal of all lymph nodes in the axilla (axillary lymph node dissection (ALND)) or radiotherapy to axilla (ART). National Institute for Health and Care Excellence (NICE) recommends ALND to patients who have a preoperative ultrasound-guided needle biopsy with pathologically proven lymph node metastases [1].

After ALND a drain is left in the wound to drain excess fluid or blood for a few days afterwards. The operation lasts one to two hours and may require an overnight stay in the hospital. This procedure delays the return to usual activities and paid work [2].

Axillary radiotherapy (ART) is radiation targeted at the axilla and is used instead of ALND in some hospitals based on local guidelines. The radiation is given five days a week for three to five weeks. Axillary radiotherapy is offered only in some specialist centres, and so patients may need to travel a considerable distance for treatment.

ALND or ART damages lymphatic drainage from the arm and both are associated with increased risk of lymphoedema, restricted shoulder movement or shoulder discomfort, pain, sensory changes and numbness[2]. These adverse effects interfere with daily activities, impair health-related quality of life (QoL) and are costly to the NHS in terms of rehabilitative treatments as they can be chronic and often irreversible with limited symptom relief.

The findings of a systematic review suggest that more than one in five women who survive breast cancer will develop arm lymphoedema [3]. Lymphoedema has a negative psychosocial impact on affected individuals resulting in negative self-identity, emotional disturbance, psychological distress, marginalization, perceived diminished sexuality and social isolation [4].

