## 2. RATIONALE

We undertook a survey to identify current clinical practice amongst breast cancer centres in the UK. Of the 70 responding hospitals, 79% performed ALND, 9% undertook ART and 12% SNB or axillary node sampling (ANS) [unpublished data]. The survey showed that clinicians are at equipoise and 99% of the respondents expressed willingness to randomise patients in the ATNEC trial.

This research question has been identified as a priority by patients at many different cancer support groups and events, including the Macmillan patient focus group, Independent Cancer Patients' Voice, Dragon's Den at the National Cancer Research Institute's (NCRI) consumer forum, NCRI Breast CSG, UK Breast Intergroup and NCRI Clinical and Translational Radiotherapy Research Working Group (CTRad). The NCRI Living with and Beyond Cancer Initiative highlights that it is important to cancer patients to live better with and beyond cancer. The number one priority concerns looking at the long-term side effects of cancer treatment, confirming the importance of this study to patients [14].

The ATNEC research question has also been identified as a key research gap by Association of Breast Surgery [15]. The UK multidisciplinary guidance published in 2019 advises that patients with no residual disease in the sentinel nodes after NACT should receive ART and recommends that clinicians should participate in the ATNEC study to answer this important research question [16]. Thus we anticipate that the study results will lead to updated NICE and specialty guidelines and will change clinical practice in the future.

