#### 6.4.7. Axillary Treatment

Participants randomised to standard care will undergo ALND or axillary radiotherapy as per local guidelines.

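### The exploratory ALND and ART subgroups are defined by treatment received, which only controls are allocated, so as worded they give no randomised comparison

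*Protocol*

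**What the plan says.** The subgroup rule is one sentence in Protocol section 10.3.3, in the paragraph on time-to-event outcomes: "Exploratory subgroup analyses will be performed for those having ALND or ART". It names no comparator and does not say how experimental participants would be placed.

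The same section sets the general principle: "All analyses will be carried out on an intention-to-treat basis to preserve randomisation, avoid bias from exclusions".

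On who can have these treatments, the Study Summary says: "Participants in the experimental arm will not receive further axillary treatment". For controls, section 6.4.7 says: "Participants randomised to standard care will undergo ALND or axillary radiotherapy as per local guidelines". Section 1 adds that ART "is used instead of ALND in some hospitals based on local guidelines".

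On how common each is, section 2 reports a survey: "Of the 70 responding hospitals, 79% performed ALND, 9% undertook ART and 12% SNB" or axillary node sampling. Section 10.1, by contrast, plans the lymphoedema comparison on the assumption that most controls have ART.

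The minimisation factors in section 6.3.3 are institution, type of breast surgery and receptor status. Intended axillary treatment is not among them. It is also not named in the data categories that section 6.5.2 lists for randomisation, nor in the schedule in Appendix 2.

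**The concern.** Membership of the subgroup is settled after randomisation and, if allocation is followed, in one arm only. A subgroup analysis keeps the protection of randomisation when it uses a characteristic that exists in both arms before allocation. Here, an experimental participant could enter either subgroup only by departing from allocation, and a control who had neither treatment would fall outside both.

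Whichever experimental participants are then chosen as comparator, the two sides may differ in hospital, in period of recruitment or in the patient features that led to ALND or ART. The control side may also differ in other treatment: section 6.4.8.2 lets ART controls have supraclavicular and internal mammary irradiation as well.

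The question is one that readers will ask. Section 10.1 quotes 5-year lymphoedema of 23% after ALND and 11% after ART, so whether omission compares well with each standard is a natural follow-up to the main result. A DFS estimate distorted by site mix could be read as reassurance against one standard and as harm against the other.

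**Working it through.** **1. Who can belong to the subgroups**

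| | Control arm | Experimental arm |
|---|---|---|
| Allocated ALND or ART | Yes, one or the other | Neither |
| What decides the type | Local guidelines | Not applicable |
| Type known before allocation for every participant | Not stated | Not stated |

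The variable named in section 10.3.3 therefore cannot be formed in both arms. This step needs no arithmetic.

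**2. The plan's own figure, used for scale**

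Inputs from section 10.1 are control 5-year DFS of 90%, a margin of 3.5 points (so 86.5%), one-sided 5% significance and 85% power.

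- Margin hazard ratio = ln(0.865)/ln(0.90) = 1.376.
- Schoenfeld events = 4 × (1.645 + 1.036)² / (ln 1.376)² = 282, which matches section 10.6.

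No stated number is wrong on this point.

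**3. What confounding could do (illustration)**

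The assumptions here are mine, not the protocol's:
- there is no treatment effect;
- 5-year DFS is 88% at ALND sites and 92% at ART sites;
- each treated control subgroup is set against the whole experimental arm.

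Let s be the share of patients at ALND sites. Then experimental DFS = s × 0.88 + (1 − s) × 0.92, and the apparent hazard ratio (experimental to control) = ln(experimental DFS)/ln(subgroup DFS).

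| s | Experimental DFS | HR against ALND subgroup | HR against ART subgroup | DFS differences (points) |
|---|---|---|---|---|
| 79/88 = 0.90 (survey, ALND and ART hospitals only) | 88.4% | 0.96 | 1.48 | +0.4, −3.6 |
| 0.50 | 90.0% | 0.82 | 1.26 | +2.0, −2.0 |
| 0.25 | 91.0% | 0.74 | 1.13 | +3.0, −1.0 |

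For example, at s = 0.50: ln(0.90)/ln(0.88) = 0.82 and ln(0.90)/ln(0.92) = 1.26.

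If the assumed gap is halved (89% and 91%), the ratios are 0.98 and 1.21 at s = 0.90, and 0.90 and 1.12 at s = 0.50. With equal prognosis every ratio is 1.00.

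**4. The ART share is uncertain**

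Applied to 950 controls, the survey's 9% gives 0.09 × 950 = about 86 ART controls. The section 10.1 assumption of an ART majority gives more than 0.5 × 950 = 475. The survey counts hospitals, not patients. These figures show subgroup size and say nothing about bias.

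**5. The same question with both arms grouped before allocation**

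In the step 3 setting, each arm would then have 88% in the ALND group and 92% in the ART group, so both hazard ratios return to 1.00. The price is precision. Split the 282 events in proportion to s, and take power at the 1.376 margin as Φ(√d × ln(1.376)/2 − 1.645), where d is the number of events:

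- s = 0.90: 253 and 29 events, power 82% and 22%;
- s = 0.50: 141 events each, power 60%;
- s = 0.25: 70.5 and 211.5 events, power 38% and 75%.

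**The case against.** The strongest reply is that section 10.3.3 gives one sentence about an exploratory analysis and leaves detail to the SAP, which is not at hand. Comparator and interaction model are ordinary SAP content. The intention-to-treat statement points away from a naive reading. Because institution is a minimisation factor, the SAP could match or stratify by site without a protocol change.

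Much of this stands. A reader might infer that the protocol plans to compare each treated subgroup with the whole experimental arm. It does not say so, and step 3 shows only what that choice could do. The sentence could also mean a description within the control arm.

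Three other stronger readings are tempting and unsupported:
- That 86 against 950 demonstrates bias. Unequal group sizes alone bias nothing, and the 9% behind the 86 conflicts with the planning assumption in section 10.1.
- That the choice of treatment is purely an institution effect. A survey of hospitals cannot show how far choice varies between patients within a hospital.
- That intended treatment is not recorded. The Randomisation Form is not reproduced, so this cannot be known.

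What does not stand is full deferral to the SAP. Section 10 requires it to be final only before the final data analysis. By then it can still use site policy, but it cannot recover what was intended for each patient before allocation unless that was written down.

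**Conclusion.** The point holds as a flaw in how the subgroups are defined. As worded, they rest on a treatment that only controls are allocated, so no comparison based on them is protected by randomisation, and the wording is inconsistent with the section's own intention-to-treat principle.

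The consequence is limited. A reader might infer a threat to the main result, but there is none: success depends on DFS and lymphoedema between the randomised arms.

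The size of any bias is unknown. Under the assumed 4-point gap in site DFS, spurious hazard ratios run from 0.74 to 1.48 across the mixes tried. The upper value passes the trial's own margin of 1.376. That range rests on the assumed gap, the assumed mix and an inferred comparator, and it collapses to 1.00 if prognosis does not differ. Confounding by institution is a well-supported inference from the references to local guidelines. Patient-level selection is possible in addition.

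This is worth correcting because the remedy is cheap and its patient-level part can be applied only while participants are still being randomised.

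**What to change.** 1. If it is not already captured, add one field to the Randomisation Form, completed before allocation for every participant: the axillary treatment (ALND or ART) intended if allocated to control. This records local practice and changes no one's treatment.
2. For participants already randomised, assign the value from documented site policy at that date. Treat sites with mixed practice as unclassified, or handle them in a sensitivity analysis.
3. Reword section 10.3.3 so that the ALND and ART subgroups are defined by this variable in both arms, and report the arm-by-intended-type interaction for DFS and lymphoedema as exploratory.
4. Label any remaining analysis by treatment received as non-randomised.

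The cost is one field, a retrospective look-up across sites and a short amendment. Intended and delivered treatment will sometimes differ, and the smaller subgroup will have low power (about 22% for DFS at the margin with a 90/10 split), so the gain is a fair estimate rather than a decisive test. If recruitment has closed, only the site-policy version remains.

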#### 3.2. Outcome

#### 3.2.1. Co-primary outcomes:

- Disease-Free Survival (DFS); defined and calculated as the time from randomisation until the date of first event of either a loco-regional invasive breast cancer relapse, distant relapse, ipsilateral or contralateral new invasive primary breast cancer or death by any cause or the censor date.
- Lymphoedema is self-reported based on two items from the validated Lymphoedema and Breast Cancer Questionnaire (LBCQ) (arm "swelling now" and arm "heaviness in the past year"). These items have been shown to be predictive of arm swelling of a 2 cm or more change in arm circumference, but provide a simpler patient-friendly measure which has been used in other studies [17-19]. Lymphoedema will be defined as 'yes' to both questions at five years.

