#### 6.5.2. Randomised participants

Primary and secondary outcome data will be collected at randomisation and then annually for at least five years (see Appendix 2- Schedule of Assessments). We are using validated questionnaires for participant reported outcomes that have been used previously. Participant demographics, medical history, tumour characteristics and details of nodal and breast surgery will be collected at randomisation. Details of any adjuvant treatment given will also be collected during follow-up.

The required follow up data will be collected by the research nurse during routine hospital visits for annual mammogram, via hospital records or through telephone follow-up calls with participants. This data will be entered into the online study database. This will ensure high compliance with follow-up, whilst minimising the burden to participants, NHS and funder. Sites are required to report participant follow-up data annually, until all participants have reached at least five years follow-up.

Participant questionnaires with questions on arm morbidity and function, health-related quality of life and health resource use will be completed either in the clinic at randomisation. Follow-up questionnaires will be posted to participants by WCTU and returned directly to WCTU. Non-responders to postal questionnaires will receive up to two reminders by post and will then be contacted by telephone for collection of core outcomes (LBCQ and EQ-5D-5L).

Participants will be consented for collection of long-term follow-up data from existing databases via data linkage, using services such as NHS Digital, Public Health England, eDRIS (Public Health Scotland) and cancer registries; this will enable us to continue to follow-up participants and report long-term recurrence and survival.

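### The main lymphoedema analysis leaves out the baseline LBCQ answers that the trial already collects, which costs precision, and no instruction makes those answers precede allocation

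*Protocol*

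**What the plan says.** Section 3.2.1 builds the lymphoedema co-primary from two LBCQ items, one on current arm swelling and one on arm heaviness over the last year, and fixes the event at a single time point: "Lymphoedema will be defined as 'yes' to both questions at five years". Status at randomisation plays no part in the definition.

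Section 10.3.3 fixes the analysis: "The proportion of patients experiencing lymphoedema at five years will be compared across trial arms using a chi-squared test", with a logistic regression to adjust for the stratification variables. The stratification variables are institution, type of breast surgery and receptor status (6.3.3, 10.3.1). Baseline LBCQ is not among them. The same section makes success depend on DFS non-inferiority together with a lymphoedema reduction of at least 5%.

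The baseline answers are nevertheless collected. Section 6.5.2 says "Primary and secondary outcome data will be collected at randomisation and then annually for at least five years", and the schedule in Appendix 2 marks the questionnaire booklet at randomisation and at months 12 to 60. Randomisation follows chemotherapy, breast surgery and a nodal procedure that removes at least three nodes (5.1, 6.3.2).

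On timing, 6.5.2 says only that the first booklet "will be completed either in the clinic at randomisation"; the word 'either' has no second option after it. Section 6.3.2 lists what must be in place before randomising (confirmed eligibility, a completed Randomisation Form and, for pathway 2, written consent). The booklet is not on that list. Once a participant is randomised, the site is emailed the allocation.

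**The concern.** Every participant has had axillary nodes removed before allocation, so some may already answer yes to both items at randomisation. If symptoms at that point predict symptoms at five years, the baseline answer is the most direct prognostic covariate in the dataset for this endpoint, and the planned analysis does not use it. The variation it could explain stays in the error term of a comparison that is sized on, and judged against, a five-point difference.

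The timing question belongs with this one. A baseline covariate may be used for adjustment, or to define a subset, only if it cannot be influenced by allocation. These are self-reported arm symptoms in a trial where participants will learn whether they are to have further axillary treatment. The protocol does not say that the booklet comes first.

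**Working it through.** **Inputs.** From Protocol 10.1 and Table 1: 1900 participants, 1:1; 25% dropout for this outcome; rates of 11% and 6%; two-sided 5%; 90% power. The baseline prevalence p0 and the correlation φ between baseline and month-60 status are not given. They are assumed below and shown as ranges.

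**1. The plan's own figure.** The usual two-proportion formula for 11% v 6% gives 652 per arm without a continuity correction and 692 with it; Table 1 has 691. Dropout: 2 × ceil(692/0.75) = 2 × 923 = 1846, as in Table 1. The design figure reproduces, and no arithmetic error is alleged.

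**2. Precision of the planned comparison.** Evaluable per arm: 1900 × 0.75 / 2 = 712.5, taken as 712.

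SE = √(0.11 × 0.89/712 + 0.06 × 0.94/712) = √(0.1543/712) = 0.0147, or 1.47 points.

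**3. Chance imbalance in baseline status.** SD = √(2 × p0 × (1 − p0)/712).

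| Assumed p0 | SD of imbalance (points) |
|---|---|
| 3% | 0.90 |
| 5% | 1.16 |
| 10% | 1.59 |

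This is imbalance in the baseline variable. It is not error in the five-year comparison.

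**4. How much of it reaches the five-year comparison.** The regression slope of month-60 status on baseline status is φ × (SD of month-60 status / SD of baseline status). Multiplying the slope by the SD in step 3 cancels the baseline SD and leaves φ × SE, whatever p0 is:

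- φ = 0.2: 0.2 × 1.47 = 0.29 points
- φ = 0.4: 0.4 × 1.47 = 0.59 points

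**5. What adjustment recovers.** Variance removed ≈ φ²; equivalent gain in participants = 1/(1 − φ²) − 1.

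| Assumed φ | Variance removed | Adjusted SE (points) | Equivalent gain |
|---|---|---|---|
| 0.2 | 4% | 1.47 × √0.96 = 1.44 | 1/0.96 − 1 = 4.2% |
| 0.4 | 16% | 1.47 × √0.84 = 1.35 | 1/0.84 − 1 = 19.0% |

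On 712 per arm, the gain is about 30 to 136 evaluable participants per arm.

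**6. Order of booklet and allocation.** Taken together, 6.3.2 and 6.5.2 allow either order. Completing the booklet after allocation is permitted; the protocol does not say that it happens.

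**The case against.** The strongest reply is that nothing in the co-primary is invalid. Randomisation takes place after surgery, so earlier symptoms are balanced in expectation. The chi-squared test keeps its type I error, and the 1.47-point standard error already includes any noise from those symptoms. Five-year prevalence by allocated arm is a legitimate target and fits the stated objective. All of that stands: this is a question of efficiency.

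Three stronger readings are tempting, and the documents do not support them.

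- **Symptoms present before allocation count as events.** They count only if both items are answered yes at month 60, and those items cover the present and the preceding year. Symptoms that resolve before then do not count.
- **Earlier symptoms leave the trial underpowered.** If 2% of both arms had persistent symptoms on top of new-onset rates of 11% and 6%, the difference would be 4.9 points and power without continuity correction would fall from 92.4% to 86.0%. But 10.1 gives 11% as an overall control-arm rate and nowhere describes either figure as new-onset only. If the rates already include such cases, planned power is unchanged.
- **A post-allocation booklet biases the planned analyses.** It cannot affect the planned lymphoedema test, which does not use baseline. Nor does the protocol describe baseline-adjusted secondary analyses: 10.3.3 names a mixed model or a standardised area under the curve, and 10.4 an area under the curve for QALYs.

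It is also fair to say that covariates are ordinary SAP content and that 10.3.3 leaves full detail to a SAP. However, the protocol itself names the test and the adjustment set, so the omission is a stated choice that a SAP would have to depart from. The order of booklet and allocation is a site procedure, and a SAP cannot restore it afterwards.

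Finally, adjusting for a baseline taken after allocation could bias a comparison that is now unbiased. That is correct, and it is why the two changes go together.

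**Conclusion.** The point holds as a loss of precision that can be avoided, with no error in the planned test. Baseline LBCQ answers are collected and left out of the main lymphoedema analysis. If they correlate with month-60 status at 0.2 to 0.4, using them removes about 4% to 16% of the variance, including a chance-imbalance component with an SD of about 0.3 to 0.6 points in a comparison whose standard error is about 1.47 points. The size rests on the assumed correlation, on 11% v 6%, and on 25% attrition. A lower correlation would give a smaller gain, and at zero there would be none. A booklet completed soon after surgery may also pick up transient swelling, which would weaken the correlation.

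The timing gap is an unstated order. It matters mainly as the condition for using the baseline safely.

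**What to change.** 1. In 10.3.3, add baseline LBCQ status (both items yes, or not) to the main lymphoedema model alongside the stratification variables, and report the adjusted marginal risk difference with its confidence interval. A risk difference standardised over the trial population stays on the scale of the five-point criterion; an adjusted odds ratio does not. State how participants without a baseline answer are kept in the analysis.
2. Add a supportive analysis in participants who do not meet the definition at randomisation.
3. In 6.5.2 and Appendix 2, state that the baseline booklet is completed and dated after surgery and sentinel node biopsy and before allocation is requested from the portal. Complete the unfinished 'either' sentence at the same time, and add the booklet to the pre-randomisation steps in 6.3.2.

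The cost is some wording, a recorded completion date and one extra step for sites before randomising. No new assessment and no extra participants are needed. If booklets have already been completed without a recorded order, their dates should be checked against randomisation before the baseline is used for adjustment.
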